#### 7.7 Visit Windows

The visit for determining the primary endpoint of insulin-independence will occur at  $75 \pm 5$  days following each islet transplant. All other visits are scheduled on a monthly basis from the last transplant (for the first 9 months; quarterly thereafter  $\pm$  14 d until 24 months, then biannually  $\pm$  30 d), and should occur within 7 days (plus or minus) of the calendar date for the transplant. For example, a subject receiving a transplant on the  $14^{th}$  of one month should have follow-up visits between the  $7^{th}$  and  $21^{th}$  of subsequent months. A second transplant resets this schedule, except for the retinal photography.

Study visits should take place within the time limits specified on the Schedule of Events (Appendix 1).

# 7.8 Post-Study Follow-up

Upon completion of the protocol-specified follow-up (Appendix 1), subjects will be asked to enroll in a separate safety/efficacy follow-up protocol. Subjects who agree to participate in the follow-up protocol and sign informed consent, will be followed for an additional (5) five years. Follow-up assessments will be conducted at pre-defined intervals as specified in the follow-up protocol. A sample schedule of events for the follow-up protocol is provided in Appendix 4. If a subject chooses to withdraw from the follow-up protocol prior to completion of the 5years, every attempt will be made to complete at Year 5 assessments immediately prior to withdrawal.

#### 8. SAFETY MONITORING

AEs that are classified as serious according to the definition set forth by the health authorities must be reported promptly to NIAID/NIDDK, Clinical Research Organization (CRO) / Data Coordinating Center (DCC), health authorities, PIs, and IRBs. This section defines the types of AEs and outlines the procedures for appropriately collecting, grading, recording, and reporting them. Information in this section complies with *International Conference on Harmonization* (ICH) Guideline E2A: Clinical Safety Data Management: Definitions and Standards for Expedited Reporting and ICH E6: Guideline for Good Clinical Practice, and applies the standards set forth in the CIT-TCAE. This document, created by the CIT Consortium, modifies the National Cancer Institute (NCI), Common Terminology Criteria for Adverse Events (CTCAE) version 3.0 (June 10, 2003), to ensure applicability in the setting of Islet Transplantation.

#### 8.1 Definitions

## 8.1.1 Adverse Event

An AE is any occurrence or worsening of an undesirable or unintended sign, symptom (including an abnormal laboratory finding), or disease that is temporally associated with the use of a medicinal product whether considered related to the medicinal product or not.

# 8.1.2 Serious Adverse Event

An SAE is defined per 21CFR§312.32 as "any AE occurring at any dose that suggests a significant hazard, contraindication, side effect, or precaution." This includes but is not limited to any of the following events:

- 1. Death.
- 2. A life-threatening event. A life-threatening event is any adverse therapy experience that, in the view of the investigator, places the patient or subject at immediate risk of death from the reaction as it occurred.
- 3. Inpatient hospitalization or prolongation of existing hospitalization. Please note that hospital admissions for the purpose of conducting protocol-mandated procedures do not need to be reported as SAEs, unless the hospitalization is prolonged due to complications.
- 4. Persistent or significant disability.
- 5. Congenital anomaly or birth defect.
- 6. An event that required intervention to prevent permanent impairment or damage. An important medical event that may not result in death, be life threatening, or require hospitalization may be considered an SAE when, based on appropriate medical judgment, it may jeopardize the subject and may require medical or surgical intervention to prevent one of the outcomes listed in this definition.

# 7. Other conditions specified in the protocol.

In addition, events that occur at a higher than expected frequency, as determined by appropriate medical judgment, may be considered SAEs.

Regardless of the relatedness of the AE to study drug, the event must be identified as an SAE if it meets any of the above definitions.

# **8.1.3** Unexpected Adverse Event

An AE is considered "unexpected" when its nature (specificity) or severity is not consistent with available product information, such as safety information provided in the package insert, the protocol, or the investigator's brochure.

## 8.2 Adverse Events

# 8.2.1 Collecting Procedure

AEs that are associated with a protocol mandated procedure, which is not part of the normal standard of care of the participant, and hypoglycemic events, will be collected beginning immediately after enrollment consent has been obtained. All other AEs will be collected beginning immediately after randomization. All AEs will continue to be collected until study completion, or for 30 days after the subject prematurely withdraws from the study. AEs will be followed until the time the event is resolved, stabilized, or the subject completes or withdraws from the study, whichever comes first.

AEs may be discovered through any of these methods:

- Observing the subject.
- Questioning the subject, which should be done in an objective manner.
- Receiving an unsolicited complaint from the subject.
- An abnormal value or result from a clinical or laboratory evaluation (e.g., a radiograph, an ultrasound, or an electrocardiogram) can also indicate an AE. If this is the case, then the evaluation that produced the value or result should be repeated until the value or result returns to normal or can be explained and the subject's safety is not at risk. If an abnormal value or result is determined by the investigator to be clinically significant, it must be reported as an AE.

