# **Safety Endpoints**

At  $75 \pm 5$  and  $365 \pm 14$  days following the first and final islet transplant:

- The incidence and severity of adverse events related to the islet transplant procedure including: bleeding (>2 g/dL decrease in hemoglobin concentration); segmental portal vein thrombosis; biliary puncture; wound complication (infection or subsequent hernia); and increased transaminase levels (>5 times upper limit of normal [ULN])
- The incidence and severity of adverse events related to the immunosuppression including: allergy; reduction in GFR; increase in urinary albumin excretion; addition or intensification of anti-hypertensive therapy; addition or intensification of anti-hyperlipidemic therapy; oral ulcers; lower extremity edema; gastrointestinal toxicity; neutropenia, anemia, or thrombocytopenia; viral, bacterial, or fungal infections; and benign or malignant neoplasms
- The incidence of a change in the immunosuppression drug regimen
- The incidence of immune sensitization defined by detecting anti-HLA antibodies not present prior to transplantation

At  $365 \pm 14$  days following the first islet transplant:

• The incidence of worsening retinopathy as assessed by change in retinal photography

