#### **Hepatic Dysfunction and Steatosis**

Transient abnormalities in liver enzyme tests have been observed immediately following intraportal islet transplantation . Three of the 86 islet transplant recipients reported to CITR have experienced transient elevations of liver enzymes requiring prolongation of post-transplant hospitalization or admission . Persistence of laboratory abnormalities indicative of liver dysfunction and likely or definitely induced by intraportal islet transplantation is a rare event; abnormalities in liver function tests (LFTs) usually resolved within 4 weeks . No correlation between the increase in LFTs and graft characteristics or graft function was found. Periportal hepatic steatosis has been described following intraportal islet allotransplantation in 20% of the studied subjects  and appears to be due to a paracrine action of insulin secreted from intrahepatic islets. More subjects with steatosis required supplementary exogenous insulin than not , suggesting that steatosis may be associated with insulin resistance and graft dysfunction. The clinical relevance of steatosis associated with intrahepatic islet transplantation remains questionable. To the best of our knowledge, there is no evidence of clinically significant, persistent liver dysfunction following intraportal islet transplantation.

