#### Safety Endpoints

At  $75 \pm 5$  days following each transplant and  $365 \pm 14$  days following the first and final islet transplant:

• The incidence and severity of AEs related to the islet transplant procedure including: bleeding (>2 g/dL decrease in hemoglobin concentration); segmental

- portal vein thrombosis; biliary puncture; wound complication (infection or subsequent hernia); and increased transaminase levels (>5 times upper limit normal [ULN])
- The incidence and severity of AEs related to the immunosuppression including: allergy; reduction in GFR; increase in urinary albumin excretion; addition or intensification of anti-hypertensive therapy; addition or intensification of anti-hyperlipidemic therapy; oral ulcers; lower extremity edema; gastrointestinal toxicity; neutropenia, anemia, or thrombocytopenia; viral, bacterial, or fungal infections; and benign or malignant neoplasms
- The incidence of a change in the immunosuppression drug regimen
- The incidence of immune sensitization defined by presence of anti-HLA antibodies absent prior to transplantation

At  $75 \pm 5$  and  $365 \pm 14$  days following the first islet transplant:

• The incidence of worsening retinopathy as assessed by change in retinal photography

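### The safety endpoint sets numeric limits for bleeding and transaminases, but sections 8.1.1 and 8.2.1 do not agree on whether crossing a limit is an adverse event, so a crossing may go unrecorded

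*Protocol*

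**What the plan says.** Section numbers refer to the CIT-05 protocol.

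- **Endpoint (Synopsis and 3.1.1, Safety Endpoints).** The unit counted is an event: "The incidence and severity of adverse events related to the islet transplant procedure including" a list of components. Two of them carry laboratory limits: "bleeding (>2 g/dL decrease in hemoglobin concentration" and "increased transaminase levels (>5 times upper limit of normal [ULN".
- **Definition (8.1.1).** "An AE is any occurrence or worsening of an undesirable or unintended sign, symptom (including an abnormal laboratory finding), or disease". Clinical significance is not a condition.
- **Collection (8.2.1).** An abnormal value is one of several ways in which an event may come to light. The instruction to the site is: "If an abnormal value or result is determined by the investigator to be clinically significant, it must be reported as an AE".
- **Recording and grading (8.2.2, 8.2.4.1).** All adverse events are recorded, reported and graded, whatever their severity or cause.
- **Attribution (8.2.4.2).** The site investigator decides relatedness for each adverse event.
- **Expected liver course (1.5.3.3).** The protocol describes transient enzyme changes directly after intraportal infusion and says that "abnormalities in liver function tests (LFTs) usually resolved within 4 weeks".
- **Data (7.5, Appendix 1, 11.1).** Blood counts and liver tests are drawn every 6 to 12 hours for 48 hours after infusion and then at scheduled visits. Laboratory results are transferred to the electronic case report form.

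**The concern.** The two limits are objective, yet a laboratory value enters the endpoint only as an adverse event. The one explicit reporting trigger for such a value is the investigator's view of its clinical significance, in an open-label trial at a single center. The definition in 8.1.1 does not contain that condition. A site that treats the sentence in 8.2.1 as its working rule could leave off a value that crosses the endpoint's own limit.

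This is most plausible for transaminases. An investigator who expects a rise that settles within weeks may well judge it not significant, even above 5 times the upper limit.

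Three things are at stake: the incidence reported for this endpoint, the attribution that the endpoint requires, and the completeness of the adverse event listings that section 8.3.3.4 sends to the monitoring board.

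**Working it through.** The protocol states no expected incidence for these events, so there is no planned figure to reproduce. The check is mainly a comparison of the text, with simple arithmetic for scale.

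**1. Is a limit crossing an adverse event?** Under 8.1.1 an undesirable abnormal finding is one, with no further test. Under 8.2.1 an abnormal value may indicate one and must be reported if judged clinically significant. If 8.1.1 governed alone, the condition in 8.2.1 would be redundant. If 8.2.1 is the working rule, it narrows 8.1.1. The text does not say which applies.

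**2. Does 8.2.2 or 8.2.4.1 settle it?** Not by itself. The duty to record and grade every adverse event begins once something is an adverse event, which is the open question.

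**3. Does the endpoint wording settle it?** It lists the two crossings as examples of procedure-related adverse events. That supports counting them, but it gives the site no recording instruction.

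**4. What is lost if a crossing is not recorded?** The value itself remains in the database (7.5, Appendix 1, 11.1), so a count of crossings can be recovered. Attribution cannot be recovered in the same way, because under 8.2.4.2 it is assigned to an adverse event. The crossing would also be absent from the adverse event listings.

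**5. Scale.** Section 10.4 sets n = 12. One subject is 1/12 = 8.3 percentage points. Exact (Clopper-Pearson) 95% intervals for x of 12, with lower bound the 2.5% quantile of Beta(x, 13 − x) and upper bound the 97.5% quantile of Beta(x + 1, 12 − x), are:

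- 4/12 = 33.3% (9.9% to 65.1%)
- 3/12 = 25.0% (5.5% to 57.2%)
- 2/12 = 16.7% (2.1% to 48.4%)
- 1/12 = 8.3% (0.2% to 38.5%)
- 0/12 = 0% (0% to 26.5%)

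*Assumed illustration:* if 4 subjects cross 5 times the upper limit and 2 transient rises are not reported, the reported incidence is 16.7% instead of 33.3%.

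*Chance of a loss, also assumed:* if each of k crossings is reported independently with probability s, the probability of missing at least one is 1 − s^k.

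- k = 2: 1 − 0.75² = 0.44 and 1 − 0.50² = 0.75
- k = 4: 1 − 0.75⁴ = 0.68 and 1 − 0.50⁴ = 0.94

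Neither the counts nor the reporting probabilities come from the protocol.

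**The case against.** The strongest reply is that 8.2.1 says *if*, not *only if*. It gives a sufficient condition for reporting, within a list of ways in which events may be found, and nowhere permits an abnormality judged not significant to be omitted. Read together, 8.1.1, 8.2.2, 8.2.4.1 and the endpoint wording can be taken to require recording. Grading follows the CIT-TCAE, whose laboratory criteria are not reproduced in the protocol. The values are captured in any case, and their derivation may be specified in the analysis plan, which is not shown.

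Much of this stands. A reader might infer that the protocol excludes crossings judged not significant; the text does not say so. A reader might also infer that the harm rates are biased downward. That is possible but not shown, since it requires sites to set 8.1.1 aside. Nor do the documents support a claim that the rates cannot be compared with other CIT-07 centers. Section 10.2.2 compares the secondary responses with CIT-07 subjects at the same institution, and CIT-07's adverse event rules are not given. Open-label assessment is the stated design, not a failure of blinding.

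A further objection concerns the remedy. Counting every hemoglobin fall above 2 g/dL through Day 365 as bleeding would bring in anemia from immunosuppression. The endpoint lists that separately, and section 1.5.2.4 reports anemia in 33% of kidney recipients on sirolimus against 21% on placebo. This is correct, and it limits how the laboratory count should be defined.

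The ambiguity remains after all of this. No sentence makes a limit crossing count in itself, and an analysis plan cannot supply an attribution that the site never made.

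**Conclusion.** The point holds as an inconsistency between the endpoint definition, 8.1.1 and 8.2.1. Section 8.2.1 can be read as a filter on laboratory values, so a transient crossing may be left off the adverse event form, go without attribution and be missing from an incidence based on those forms. Each subject so missed costs 8.3 percentage points at n = 12. How many would be missed is unknown.

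The conclusion rests on two assumptions: that the incidence is taken from adverse event reports, as the endpoint's wording suggests, and that at least some sites or investigators would apply 8.2.1 as the working rule. It does not rest on any claim that events have been or will be suppressed.

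**What to change.** 1. **Recording rule.** Reconcile 8.1.1 and 8.2.1 with one sentence: a value crossing a limit named in the safety endpoints is always recorded as an adverse event and attributed, whatever its judged clinical significance.

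2. **Laboratory-based count.** Report the hemoglobin and transaminase components also from the blood count and chemistry results already collected. Restrict the count to a pre-specified period after each infusion and assess it relative to the pre-infusion value. Show it beside the investigator-attributed events, so that later drug-related anemia or enzyme rises are not counted as procedure events.

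The cost is one protocol sentence, a stated post-infusion period and one derived-variable program. Treatment, visits and samples do not change. The downside is that some transient, asymptomatic rises will be counted, so the reported rates may look slightly less favorable.

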## **8.2.2** Recording Procedure

Throughout the study the investigator will record all AEs on the appropriate AE case report form (CRF) regardless of their severity or relation to study medication or study procedure. The investigator will treat subjects experiencing AEs appropriately and observe them at suitable intervals until their symptoms resolve or their status stabilizes.

# 8.2.3 Reporting of AE Information Following Study Completion

Collection of safety information following the end of investigational product administration is important in assisting in the identification of possible delayed toxicities or withdrawal effects. In this trial, all SAEs must be collected that occur within 30 days following discontinuation of dosing. In addition, the investigators should report any SAE that may occur after this time period which they believe to be certainly, probably, or possibly related to the investigational product. Finally, all events of death, graft loss, malignancy, PTLD, and serious infections (i.e., otherwise meeting SAE reporting requirements) must be reported for all randomized subjects until the end of the study, irrespective of study drug discontinuation or investigator-deemed causality.

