# 8.3 Serious Adverse Events

# **8.3.1** Collecting Procedure

SAEs will be collected following the subject's signing of the enrollment consent until 30 days after the subject completes or withdraws from the study. SAEs will be followed until the time the event is resolved, stabilized, or until 30 days after the subject completes or withdraws from the study, whichever comes first.

In addition, SAEs that occur after this time period that are believed to be certainly, probably, or possibly related to the investigational agent will be collected.

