#### REDUCED FOLLOW-UP SCHEDULE

Complete the following assessments at the intervals (+/-7 days) indicated below relative to the day the subject discontinued study treatment. Continue conducting these assessments at the defined intervals until the subject reaches one year post **last** transplant.

- Assess SAEs and hypoglycemic events: q1 month. If subject does not come to the study site for the visit, attempt to obtain information via a phone contact.
- Alloantibody (central lab): q 1 month for the first 3 months and q 3 months thereafter.

Complete the following assessments at 1 year (+/- 14 days) post **initial** transplant:

- Assess SAEs and hypoglycemic events
- Alloantibody (central lab)
- HbA1c (central lab)
- 90 minute c-peptide post MMTT (central lab)
- Serum creatinine (central lab)
- QOL questionnaire (via mail or in-person)

Complete the following assessments at 1 year (+/- 7 days) post **last** transplant:

- Assess SAEs and hypoglycemic events
- QOL questionnaire (via mail or in-person)

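### For subjects who stop treatment but stay in the study, the AE and SAE collection rules conflict; if Appendix 2 governs, later non-serious AEs are not solicited and Day 365 incidence can be under-counted

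*Protocol*

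**What the plan says.** **Who is affected.** Section 5.7.2 keeps subjects who stop study treatment in the study to its normal end, for safety and efficacy monitoring, and moves them to Appendix 2. Section 7.5.1 sends a second group there: those without a functioning graft who do not qualify for another transplant. Stopping treatment is therefore not withdrawal from the study.

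**All AEs.** Section 8.2.1: "All AEs will continue to be collected until study completion, or for 30 days after the subject prematurely withdraws from the study". Section 8.2.2: "Throughout the study the investigator will record all AEs on the appropriate AE case report form (CRF) regardless of their severity". Both are tied to the study, not to treatment.

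**SAEs.** Section 8.3.1: "SAEs will be collected following the subject's signing of the enrollment consent until 30 days after the subject completes or withdraws from the study". Section 8.2.3 differs: "In this trial, all SAEs must be collected that occur within 30 days following discontinuation of dosing". After that it asks for SAEs the investigator thinks at least possibly related, plus a fixed list (malignancy, PTLD, serious infection, graft loss, death) that "must be reported for all randomized subjects until the end of the study, irrespective of study drug discontinuation or investigator-deemed causality".

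**Reduced schedule.** Appendix 2: "Assess SAEs and hypoglycemic events: q1 month", continued to one year after the last transplant. It also has alloantibody at intervals and, one year after the first transplant, HbA1c, stimulated c-peptide, serum creatinine and quality of life. It has no line for non-serious AEs and no CBC, lipids, urine albumin or measured GFR.

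**What the data feed.** The safety endpoints in Section 3.1.1, assessed among other times at Day 365 after the first and final transplant, include "The incidence and severity of AEs related to the immunosuppression including: allergy; reduction in GFR; increase in urinary albumin excretion", and go on to mouth ulcers, leg edema, gut toxicity, cytopenias and infections. Section 10.1 puts every transplanted subject in the safety analysis.

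**The concern.** A site looking after a subject who has stopped sirolimus finds two instructions for non-serious AEs and two for SAEs. Many of the Day 365 toxicity endpoints are usually non-serious, and Appendix 2 does not ask about non-serious events. A site that follows the appendix collects less on exactly the subjects who have left the regimen, while those subjects stay in the denominator. An AE that nobody asked about leaves no missing value behind. The promise in Section 10.2.2 to report how often secondary data are missing will therefore not reveal the gap, and the subject simply appears not to have had the event.

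**Working it through.** The protocol states no figure on this point, so the check is a comparison of texts followed by a short illustration.

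**Step 1. Non-serious AEs after stopping**

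| Source | Events | Until |
|---|---|---|
| 8.2.1, 8.2.2 | all AEs, any severity | study completion |
| Appendix 2 | SAEs and hypoglycemic events | one year after last transplant |

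The appendix line is not shorthand. The matching row in Appendix 1 covers AEs, hypoglycemic events and toxicity together, so the narrower line changes the content. The two sources conflict.

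**Step 2. SAEs after stopping**

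| Source | Events | Until |
|---|---|---|
| 8.3.1 | all SAEs | 30 days after study completion or withdrawal |
| Appendix 2 | SAEs, monthly | one year after last transplant |
| 8.2.3 | all SAEs | 30 days after end of dosing; then related SAEs and the fixed list |

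Section 8.2.3 is the outlier. For a single transplant with treatment stopped on day d, its full window ends at d + 30 and that of 8.3.1 at 365 + 30 = 395. The gap is 395 − (d + 30) = 365 − d days: 290 days for d = 75 and 185 days for d = 180.

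Sections 8.2.1 and 8.3.1 do not conflict. They cover different event classes, and both are tied to the study; SAEs simply have a 30-day tail.

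**Step 3. Time with no scheduled question about non-serious AEs, if Appendix 2 governs**

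The share for one subject is (365 − d)/365. For k of 12 subjects the share of cohort time is k(365 − d)/(12 × 365). Both k and d are assumptions.

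| d | one subject | k = 1 | k = 4 |
|---|---|---|---|
| 75 | 290/365 = 79.5% | 290/4380 = 6.6% | 1160/4380 = 26.5% |
| 180 | 185/365 = 50.7% | 185/4380 = 4.2% | 740/4380 = 16.9% |

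**Step 4. Effect on an incidence**

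With the 12 subjects of Section 10.4, one subject whose only event of a given type is missed moves the incidence by 1/12 = 8.3 points. A true 6/12 would read 5/12 or 4/12. The exact intervals below match those tabulated in Section 10.4 for the same counts.

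| Count | Incidence | Exact 95% interval |
|---|---|---|
| 6/12 | 50% | 21% to 79% |
| 5/12 | 42% | 15% to 72% |
| 4/12 | 33% | 10% to 65% |

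The shift is small beside the width of these intervals, but it goes in one direction only.

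**The case against.** The strongest reply is that collection is already required. Sections 8.2.1, 8.2.2 and 8.3.1 apply to everyone still in the study, and unsolicited complaints and observation count as sources. Appendix 2 is a schedule and does not claim to override Section 8, and Section 8.2.3 can be read as a minimum. This stands in part: the under-count is conditional on a site working from the appendix, or from 8.2.3 alone. It does not remove the conflict. The protocol gives no order of precedence, and a visit schedule is what a site works from. The reading of 8.2.3 as a minimum is also awkward, because its fixed list to the end of the study would be redundant if all SAEs were already being collected that long.

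Several stronger readings are tempting, and the documents do not support them:

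- **That toxicity causing a stop is lost.** That event happens before the move to Appendix 2, is collected under 8.2.1, and remains in a cumulative Day 365 incidence. Only later events are at risk. The protocol also gives no rate of stopping and no indication that non-serious toxicity is a frequent reason.
- **That Appendix 2 collects SAEs and nothing else.** It also has hypoglycemic events, alloantibody and year-one creatinine, so sensitization and a creatinine-based view of renal function remain.
- **That full SAE collection closes near Day 36** (last rituximab dose on Day +6, plus 30). This takes dosing to mean the investigational product alone. Section 8.2.3 also speaks of study drug, and Section 4.3.1 uses that term for the immunosuppressive medication, so 30 days after stopping immunosuppression is the more natural reading.
- **That the comparison with CIT-07 is biased.** That study's stopping and collection rules are not shown.

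One practical objection stands in full: a phone call cannot detect cytopenia, albuminuria or a fall in measured GFR.

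**Conclusion.** The point holds as a conflict of rules with a conditional consequence. There are two contradictions for subjects who stop treatment or lose graft function but stay in the study: 8.2.1 and 8.2.2 against Appendix 2 on non-serious AEs, and 8.2.3 against 8.3.1 and Appendix 2 on SAEs.

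If Appendix 2 governs, non-serious events that start after stopping are not solicited, and Day 365 incidence among all transplanted subjects can be under-counted by 8.3 points per subject missed. That size assumes the missed event is the subject's only one of its type. The total effect cannot be stated without a discontinuation rate. SAEs are at risk only if 8.2.3 is applied alone, and even then related SAEs and the listed events are kept.

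This should be corrected, because the change is cheap and the safety endpoints depend on it. It does not touch the primary endpoint.

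**What to change.** 1. State one rule in Sections 8.2.1, 8.2.3, 8.3.1 and Appendix 2: all AEs to study completion, and all SAEs to 30 days after completion of or withdrawal from the study, whether or not treatment was stopped.
2. Delete the limit of 30 days after dosing from Section 8.2.3. Its requirement for related SAEs arising after the window can stay.
3. Change the Appendix 2 assessment line to cover AEs, SAEs and hypoglycemic events, at the monthly contact and at the two one-year assessments.
4. Appendix 2 schedules no CBC, lipids, urine albumin or measured GFR. For endpoints that rest on these, report that they were not systematically assessed after stopping, with the number of subjects concerned, and do not count those subjects as event-free.

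The cost is a wording amendment and slightly more AE entry for the subjects who stop. No visit is added, since the monthly contact already exists and may be by phone. The remedy is partial for laboratory-detected events, which is why item 4 is needed.
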